7.2.2 Safety Analyses

Safety endpoints will be analysed on the Safety set.

Ocular and systemic adverse events (AEs)

Ocular and systemic AE reported during the investigation will be coded using the Medical Dictionary for Regulatory Activities (MedDRA dictionary).

Summary tables will be performed on Treatment-Emergent AEs (TEAEs).

Ocular and systemic TEAEs will be analysed separately on the basis of the localisation and System Organ Class (SOC).

TEAEs are AEs that occurred after the first IMP instillation. For the AEs that occurred the day of the first IMP instillation, a question on the eCRF will establish the timing compared to the first instillation.

Separate descriptions of ocular (for both, study and contralateral eye together) and systemic TEAEs will be performed by treatment group:

- An overall summary of the number and percentage of patients experiencing at least one AE, SAE, IMD-related AE, IMD-related SAE and AE leading to premature investigation IMD discontinuation.
- Number and percentage of patients experiencing at least one AE, as well as the number of AEs, by SOC and Preferred Term (PT). The summaries will be performed for AEs leading to premature IMD discontinuation.
- Number and percentage of patients with AEs, by SOC, PT and severity.

- Number and percentage of patients with AEs, by SOC, PT and relationship to IMD.

[figure not shown]
Documented list of individual data concerning TEAEs will be performed.

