6 DESIGN OF THE CLINICAL INVESTIGATION

6.1 GENERAL

6.1.1 Justification of the Investigation Design

Methodology: a 5-week, international, multicentre, randomised, investigator-masked, 2 parallel groups (T2769 versus Hylo-Forte®) investigation.

- Multicentre

The investigation will be performed in different sites in EU.

A multicentre (and multi-investigator) design will provide the possibility of recruiting the patients from a wider population than a single-centre design and of using the device in a broader range of clinical settings, thus presenting an experimental situation that is more typical of future use. In this case, the involvement of a number of investigators also gives the potential for a wider range of clinical judgments concerning the value of the therapeutic intervention. In addition, it is also a practical means of accruing sufficient patients to satisfy the investigation objective.

- Randomised

At the randomisation visit on Day 1, a patient fulfilling all eligible criteria will be randomly assigned to 1 of the 2 treatment groups (T2769 or Hylo-Forte®). Randomisation ensures the investigator remains masked to product assignment for DES treatment. It is generally considered the most reliable method for evaluating the effects of interventions.

- Choice of run-in period

Patients meeting the screening criteria will undergo a 7-10-days run-in period. During this period, all patients will substitute their current dry eye treatment with Hydrabak®, ophthalmic solution containing NaCl 0.9%. Patients will instill 1 drop in each eye, from 3 to 6 times daily.

[Redacted content block] (Baudouin et al. 2017; Chiambretta et al. 2017; Labetoulle et al. 2018; Holland et al. 2019).

- Investigator-masked

A double-masked investigation design is not possible due to different commercial packaging between T2769 – Hylo-Forte®.

However, the identity of the IMD given to each patient will not be known for the masked investigator who is independently in charge of the ophthalmic examination.

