As per literature, 1 month is a standard approach, commonly considered enough to assess a product performance in dry eye. In addition, in the previous clinical investigation on T2769 conducted by Laboratoires THÉA (CIR LT2769-001/17E1044), the improvement was rapidly observed after 14 days of treatment (see Section 3.3).

[figure not shown]
Thus, the change from baseline (D1) in total ocular surface staining grade according to Oxford 0-15 grading scheme^b (corneal staining by fluorescein and conjunctival staining by fluorescein with a yellow filter at D36 in the study eye^c) was set as the primary performance endpoint to evaluate the performance of the treatment.

Different ocular surface staining scales have been developed and despite common usage, a universally accepted “gold standard” grading scale does not exist for corneal and conjunctival staining. This investigation will use the Oxford scale, a widely used and standardised grading scale. International regulatory agencies such as the Food and Drug Administration (FDA) rely on corneal and conjunctival staining measurement as a primary endpoint in clinical trials of commercially registered dry eye treatments (Begley et al. 2019).

^abaseline is defined as the assessment at randomisation visit before the first IMD instillation. Missing value at randomisation visit will not be replaced.

^bthe analysis will be performed following original oxford scale [REDACTED]

[figure not shown]
[figure not shown]
^cdefined in the statistical considerations section (see Section 7.2).

6.1.2.8 *Safety Endpoints*

The following safety [REDACTED] endpoints will be assessed:

- Treatment-Emergent Adverse Events (TEAEs) by System Organ Class and Preferred Term (separately for ocular and systemic TEAE).

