14 ADVERSE EVENTS, AND INCIDENTS

14.1 DEFINITION OF ADVERSE EVENT (AE)

Adverse Event (AE): Any untoward medical occurrence, unintended disease or injury or untoward clinical signs (including abnormal laboratory finding) in subjects, users or other persons whether or not related to the IMD.

NOTE:

- This definition includes events related to the IMD or the comparator
- This definition includes events related to the procedures involved
- For users or other persons, this definition is restricted to events related to the use of the IMD or comparator.

NOTE:

- Adverse event is an incident.

Treatment-Emergent AE (TEAE): AE that occurs or that worsens in severity after at least one dose of IMD has been administered/applied.

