14.5 RECORDING AES

AEs recording and reporting will extend from signing of informed consent until the final visit. If the investigator is aware of an AE occurring within one month after final investigation visit and that he/she considers there is a causal relationship with the IMD, the AE should be recorded in the e-CRF. An incident form must also be recorded by the unmasked collaborator.

The investigator shall:

- a) Record all AEs, regardless of the relationship to IMD and seriousness, in the e-CRF together with an assessment. For each AE, a corresponding incident form must also be recorded by the masked collaborator.
- b) Supply the Sponsor, upon Sponsor's request, with any additional information related to the safety reporting of a particular event.

All AE reports should contain: a brief description of the event (diagnosis, localisation ...), date and time of onset (if needed), duration (hours or days), intensity of symptoms (severity), treatment required, relationship with IMD and CIP procedure, action taken with the IMD, outcome, date and time of resolution and whether the event is classified as serious.

If there is a worsening of a medical condition that was present before starting the clinical investigation, this should be considered as a new AE and a complete evaluation should be recorded.

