- Number and percentage of patients experiencing at least one serious TEAE, as well as the number of serious TEAEs, by SOC and PT – ocular and systemic AEs together.
- Number and percentage of patients experiencing at least one non-serious TEAE, as well as the number of non-serious TEAEs, by SOC and PT – ocular and systemic AEs.
- Number and percentage of patients experiencing at least one non-serious TEAE with PT occurring for at least 5% of the patients, as well as the number of non-serious TEAEs, by SOC and PT – ocular and systemic AEs.

Individual data listings will include all collected information, i.e. brief description of the event (diagnosis, localisation etc.), date and time of onset, time to AE occurrence, duration (days), intensity of symptoms (severity), treatment required, relationship with IMD and CIP procedure, action taken with the IMD, outcome, date and time of resolution and whether the event is classified as serious. [REDACTED]

Individual data listings that will be provided are:

[figure not shown]
- TEAEs – separately the ocular and systemic
- Non-TEAEs
- STEAEs
- TEAE leading to premature IMD discontinuation

This document is confidential.

Statistical Analysis Plan

Sponsor: Laboratoires Théa; Clinical Investigational Plan No.: LT2769-004

All aforementioned analyses will be performed in the SAF set, apart from the non-TEAEs listing which will be created in the Enrolled set.

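### CIP 7.2.2 omits worsening from its TEAE definition although CIP 14.1 includes it, so a run-in AE that worsens on the device can be left out of the TEAE tables, depending on how it is recorded

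*Protocol*

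**What the plan says.** CIP 7.2.2 (Safety Analyses) states that "TEAEs are AEs that occurred after the first IMP instillation". For AEs on the day of first instillation it adds that "a question on the eCRF will establish the timing compared to the first instillation". It does not mention worsening. CIP 14.1 defines a TEAE as an "AE that occurs or that worsens in severity after at least one dose of IMD has been administered/applied".

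Collection starts before dosing. CIP 14.5 says "AEs recording and reporting will extend from signing of informed consent until the final visit", and CIP 6.1.1 says "Patients meeting the screening criteria will undergo a 7-10-days run-in period". During that time saline replaces the patient's usual dry eye treatment.

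Two recording rules deal with worsening. CIP 6.4.1.3.1, repeated in SAP 6.3.4.1, asks for an AE to be reported when a sign or symptom the patient already had gets worse to a clinically significant degree. CIP 14.5 goes further and makes the worsening a new AE with a complete evaluation, but that rule opens with "If there is a worsening of a medical condition that was present before starting the clinical investigation".

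TEAEs by SOC and PT, ocular and systemic separately, are the readable safety endpoint (CIP 6.1.2.8, SAP 3.2.3). The summary tables in SAP 6.3.4.1 are all built on TEAEs. The AE outputs use the Safety set, "apart from the non-TEAEs listing which will be created in the Enrolled set".

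**The concern.** The two definitions can classify the same patient differently. Someone programming tables from 7.2.2 and someone reviewing safety data with 14.1 in hand may not agree on who had a TEAE.

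The design makes the case plausible. Patients stop their usual drops for 7-10 days, AEs are collected throughout, and the foreseeable device effects in CIP 14.9 (irritation, redness, burning, stinging, foreign body sensation) are of a kind that could also begin in the run-in. If such an AE was mild at Visit 2, became severe on the device and kept its run-in onset date, the 7.2.2 rule would keep it out of the tables by severity, relationship, seriousness and discontinuation. It would be seen only in the non-TEAE listing, even if it led the patient to stop the device. If one product made such events worse more often than the other, the omission would fall more heavily on that arm.

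**Working it through.** The plan states no figure on this point, so the check is to take each kind of event and apply the recording rules first and the two definitions second. The IMP in 7.2.2 is read as the IMD.

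| Event | Recording rule that applies | TEAE under 7.2.2? | TEAE under 14.1? |
|---|---|---|---|
| (a) AE starts after first instillation | Ordinary AE recording | Yes | Yes |
| (b) Condition present before the investigation worsens after first instillation | 14.5: recorded as a new AE | Yes | Yes |
| (c1) Run-in AE, clinically significant worsening after first instillation, entered as a new record | 6.4.1.3.1 and SAP 6.3.4.1 | Yes | Yes |
| (c2) As (c1), but the grade is raised on the existing record | 6.4.1.3.1 and SAP 6.3.4.1, which do not say that a new record is opened | No | Yes |
| (d) Run-in AE whose grade rises after first instillation without being judged clinically significant, with no new record | None that requires a separate AE | No | Yes |

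Three steps support rows (c2) and (d).

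1. The new-AE rule in 14.5 does not clearly reach a run-in AE. It is limited to conditions that pre-date the investigation. CIP 6.3.4 places enrolment at signature of consent, and the run-in follows that.
2. The rule in 6.4.1.3.1 has a higher threshold than 14.1. Section 14.1 asks only for worsening in severity, which on the three-grade scale of 14.4.1 can be a single step. Section 6.4.1.3.1 asks for clinical significance.
3. The Day 1 question is described only as fixing when an AE that occurred that day fell relative to the first instillation. Nothing says it is also asked about the worsening of an AE that was already open.

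Size of one misclassified patient: 74 randomised patients at 1:1 (CIP 6.1.7, 6.1.2.1) give 74 / 2 = 37 per arm. If all are dosed, one patient is 1 / 37 = 0.027, or 2.7 percentage points of an arm's TEAE rate. A patient who has another TEAE anyway would change only the rows for that SOC or PT, not the overall rate.

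The expected number of such patients would be 74 × P(run-in AE open at first instillation) × P(it worsens on the device) × P(no new record is made). The documents give none of the three probabilities, so no count is offered.

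**The case against.** The strongest reply is that the recording rules already do the work. Section 6.4.1.3.1 does not confine pre-existing signs and symptoms to those present before consent, and SAP 6.3.4.1 repeats it in the section that specifies the tables. A mild event that becomes severe would ordinarily count as clinically significant worsening. Once it is reported as an AE after dosing, it satisfies 7.2.2 as well. Where the run-in event is dry eye itself getting worse, the condition was there at entry (inclusion criterion 1.3), and 14.5 makes its worsening a new AE. This stands. A reader might infer that run-in AEs that worsen on the device are lost as a rule; the documents do not support that.

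A second reply concerns what cannot be seen. CIP section 7 leaves detailed methods to the SAP, and the AE section of the SAP is partly redacted, so a definition that includes worsening may be there. A reader might infer that the SAP fails to define TEAE; the readable text cannot show that. The eCRF completion guidelines (CIP 6.5.3) and the wording of the Day 1 question are also not available. That a site might update an existing record is therefore a possibility left open, not something the documents describe.

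A third reply is that the consequence is modest. The TEAE summaries described are counts and percentages, one rule applies to both arms, and tolerability is also measured by post-instillation symptoms, visual acuity and tolerance ratings by patient and investigator. This limits the importance of the point, but it does not remove the conflict between 7.2.2 and 14.1. Nor does applying one rule to both arms guarantee equal loss if the products differ in how often they worsen an existing event.

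**Conclusion.** The inconsistency is real and lies in current CIP text: 7.2.2 gives a narrower safety endpoint than the CIP's own definition in 14.1. Its practical reach is limited to run-in AEs that worsen after the first instillation without a new record, either because the site raises the grade on the existing entry or because the rise is not judged clinically significant. For those events, inclusion in the TEAE tables depends on data-entry practice, which a pre-specified endpoint should not leave open.

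How many patients are affected cannot be estimated from the documents. Each one who has no other TEAE is worth about 2.7 percentage points in an arm of 37, assuming all randomised patients are dosed. The conclusion also assumes that the tables are programmed from the 7.2.2 sentence; if redacted SAP text already adopts the 14.1 definition, the remaining work is to correct the CIP sentence and settle the recording rule. The point merits correction but does not bear on the primary non-inferiority analysis.

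**What to change.** Replace the 7.2.2 sentence with the 14.1 definition: a TEAE is an AE with onset, or an increase in severity, after the first IMD instillation. Use the same definition in SAP 6.3.4.1 unless the redacted text already does.

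State in the eCRF completion guideline that when an AE open at first instillation later increases in severity, the increase is entered as a new record dated at the worsening. Apply the Day 1 timing question to worsening as well as to onset.

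The cost is one sentence in the CIP and SAP, one line in the guideline and a small programming change. The downside is a possibly slightly higher TEAE count.

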7.3 ANALYTICAL PROCEDURES

[figure not shown]
Quantitative variables (Continuous data) will be summarised in summary tables indicating the number of non-missing/missing observations (n), mean, SD, median, first quartile (Q1), third quartile (Q3), minimum and maximum, and 95% Confidence Interval (CI) of the mean/median.

Qualitative variables (Categorical data) will be summarised in summary tables indicating the number of non-missing/missing observations (n), count and percentage of each modality, and 95% CI.

[figure not shown]

7.5 SAMPLE SIZE CALCULATION AND JUSTIFICATION

The sample size is driven by the statistical hypothesis on the primary objective: to demonstrate the non-inferiority of T2769 compared to Hylo-Forte® in terms of the change from baseline (D1) in total ocular surface staining score assessed on Oxford 0-15 scale, in the study eye at the D36 visit.

7.6 RATIONALE FOR THE NUMBER OF PROCEDURES TO BE PERFORMED BY A SINGLE USER AS PART OF THE LEARNING CURVE AND HOW THESE DATA ARE TO BE ANALYSED

7.8 INTERIM ANALYSIS, CRITERIA FOR THE TERMINATION OF THE CLINICAL INVESTIGATION ON STATISTICAL GROUNDS

NA.

7.9 MANAGEMENT OF BIAS AND, WHEN RANDOMISATION, MATCHING OR BLINDING ARE APPLIED, PLAN FOR ASSESSMENT OF SUCCESS THEREOF.

[figure not shown]
The use of randomisation attempts to mitigate accidental bias (such as selection bias), promoting comparability of the study groups and serves as a basis for statistical inference for quantitative evaluation of the treatment effect.

Masking will be achieved by providing each product unit with identical cardboard box and by identifying it by an IMD kit number.

7.10 MANAGEMENT OF POTENTIAL CONFOUNDING FACTORS

[figure not shown]
Baseline value will be included in all MMRM models (if applicable) as covariate.

Other covariates will be explored and detailed in the SAP.

[figure not shown]
7.12 SPECIFICATION OF SUBGROUPS

NA.

7.15 PROCEDURES FOR REPORTING ANY DEVIATION(S) FROM THE ORIGINAL STATISTICAL PLAN

Any changes from the planned analyses will be described and justified in the SAP and the final CIR.

7.17 DEFINE A STRATEGY FOR POOLING DATA, IF APPLICABLE.

NA.

8 DATA MANAGEMENT

8.1 METHODS FOR DATA ENTRY AND COLLECTION

Each participating site will maintain appropriate medical and research records for this clinical investigation in compliance with GCP - ISO 14155:2020 sections 3.47, 3.48 and 7.8.1 and any other regulatory and institutional requirements for the protection of patient's confidentiality.

Data will be reported in an electronic data capture (EDC) system for collection of electronic Case Report Forms. CRO is responsible for the set-up and maintenance of the EDC. The EDC will be compliant with FDA 21 CFR Part 11 and EU Annex 11.

The eCRFs will be completed by the PI or delegates within the investigational sites. Entries in the eCRF shall be made complete, correct and in a timely manner.

8.2 PROCEDURES USED FOR DATA REVIEW, DATABASE CLEANING, AND ISSUING AND RESOLVING DATA QUERIES

Data Management activities will be performed by Laboratoires THÉA Data Manager and/or the CRO in charge of Data Management and will be defined in the Data Management Plan (DMP).

- Management of queries

The sponsor or representative will ensure that the reported data are consistent and complete.

Data clarifications requests, also called queries or edit checks, will be generated in the EDC by a data manager or the site's CRA.

The CRAs affected to the site can open queries for source data verification mismatch, deviation verification, safety clarifications, and when data inconsistencies are detected. The CRAs will follow and close the queries that they posted.

The Data management department will create queries based on the data validation plan as detailed in the DMP. The purpose of the clarifications will be, but not limited to, data completion request, data inconsistencies, verification of possible deviations, clarification requests on safety events. The Data management team will follow and close the queries that they posted.

The investigational sites will have to answer directly in the EDC by giving a comment and making the necessary corrections to the reported data until the query is considered as resolved by the query creator or affiliate.

No self-evident corrections will be made by the sponsor.

- Coding of events

Diagnosis for AEs and medical and surgical history will be coded using Medical Dictionary for Regulatory Activities (MedDRA). Whodrug Anatomic Therapeutic Chemical (ATC) code will be used for previous and concomitant treatment coding. Versioning will be specified in the DMP.

- Management of external data
 - The clinical database and the IRT database will be periodically reconciled to ensure that the information reported in both databases are matching.
 - The results of the Tear level of inflammatory cytokines will be sent by the central laboratory to the data management department and included in the clinical database. The clinical and laboratory databases will be reconciled as detailed in the DMP.

The investigator will cooperate with Laboratoires THÉA and any person nominated by Laboratoires THÉA to monitor or supervise the conduct of the investigation.

The investigator and authorised delegate(s) will ensure that proper data for the clinical investigation are collected and accurately documented in the appropriate sections of eCRFs.

8.3 PROCEDURES FOR VERIFICATION, VALIDATION AND SECURING OF ELECTRONIC CLINICAL DATA SYSTEMS

Laboratoire Théa will verify that the EDC provider is able to demonstrate the validity and security of the electronic tools used during the study. If necessary, security tests will be performed.

The access to the electronic data systems will be individual and protected by a personalized password.

All data entry and modifications will be stored in an audit's trail indicating who performed the action and when.

8.4 PROCEDURES TO MAINTAIN AND PROTECT PATIENT PRIVACY

Laboratoires THÉA, as Sponsor of the clinical investigation, acting as data controller and is committed to protecting the privacy and security of personal data processed for the purposes of the clinical investigation under the conditions define below:

- Compliance with the General Data Protection Regulation (GDPR) and other applicable law or regulation:**

Laboratoires THÉA is committed to comply with the Regulation (EU) 2016/679 of the European Parliament and of the Council of 27 April 2016 on the protection of natural persons with regard to the processing of personal data and on the free movement of such data, and repealing Directive 95/46/EC (hereinafter the General Data Protection Regulation "GDPR") and any other applicable law or regulation related to the protection of personal data.

It is specified that for the clinical investigation, Laboratoires THÉA also comply with the applicable guidelines of the French supervisory authority ("Commission Nationale de l'Informatique et des Libertés" hereinafter the "CNIL") as defined in the deliberation n°2019-153 of 3 May 2019 of the CNIL, also called the "MR-001".

- Data subjects information on the processing of their personal data**

The data subjects namely the patients and the investigator, including the personnel working with the investigator, are informed of the collection and processing of their personal data for the realisation of the clinical investigation.

In particular, the patients are informed by the investigator during the delivery of the Informed Consent Form (ICF) where all the mandatory information of Article 13 of the GDPR are provided.

- Data subjects exercise of their rights on their data**

The data subjects, namely the patients and the investigator, including the personnel working with the investigator, have the right, under the conditions and within the limits provided by the regulations, to access, rectify, delete or determine guidelines as to the use of their personal data after their death, as well as the right to oppose or request the limitation of processing.

In addition, and according with article L1111-7 of the French Public Health Code, the patients can access to their personal data by asking to the investigator.

For all requests concerning the rights of the patients regarding their personal data, they are advised to contact the investigator who will in turn contact Laboratoires THÉA. Otherwise, Laboratoires THÉA named a Data Protection Officer who can be contacted by the patients.

The data patients, namely the patients and the investigator, including the personnel working with the investigator, have the right to bring a complaint with the supervisory authority, namely the CNIL in France and/or local equivalent of CNIL.

8.5 METHODS FOR DATABASE LOCKING AT THE START OF THE ANALYSIS AND STORAGE UPON COMPLETION OF THE CLINICAL INVESTIGATION

The database lock consists in the removal or changing of user access for database to prevent any further changes to the data. The database lock enables data collected to be used for formal analysis or submission to a regulatory authority. Database lock occurs following the conduct of the clinical investigation.

Database will be locked when all data will be entered and clean. Data Management CRO coordinates the activities around Database Lock, including completing the Database Lock Checklist, managing Database Lock Form, and ensuring archival activities are complete.

